1.2.1.2.2 Clinical safety of pasireotide s.c. and LAR

Pasireotide s.c.

Single and multiple doses of pasireotide s.c. have generally been well tolerated by healthy volunteers. The most commonly reported adverse events (AEs) were GI related such as mild diarrhea and nausea, requiring no treatment or study discontinuation. The frequency of these AEs appeared to decrease overtime in multiple-dose studies.

Hyperglycemia was the most important side effect and was observed across all indications. Blood glucose tended to rise with increasing dose, and appeared to be more notable in patients who had a history of hyperglycemia or diabetes mellitus prior to receiving pasireotide. However, hyperglycemia in these patients was responsive to appropriate diabetic management such as adjustments in oral antidiabetic treatment, or in some cases the addition of insulin.

Pasireotide's effect on QT prolongation was demonstrated by two thorough QT (TQT) studies [\[SOM230B2113\]](#) and [\[SOM230B2125\]](#). The second TQT study SOM230B2125 was designed to evaluate the effect of pasireotide on cardiac intervals using an individualized correction method to account for the known bradycardic effect of pasireotide. It was conducted as a follow-up to Study SOM230B2113, which showed that pasireotide at the Maximum Tolerated Dose (MTD) of 1950 µg b.i.d dose induced prolongation of QTcF, whereas no relevant effect on QTcB was observed. The second TQT study confirmed an effect of pasireotide on QTcI of pasireotide at both the 600 µg bid and the 1950 µg bid dose. The maximal placebo-subtracted change from baseline in QTcI was seen at 2 hours post dose, at which time the mean (90% CI) difference was 13.19 ms (11.38; 15.01) for pasireotide 600 µg bid, and 16.12 ms (14.30; 17.95) for pasireotide 1950 µg b.i.d. Both pasireotide doses decreased heart rate, with a maximal difference to placebo observed at 1 hour for pasireotide 600 µg b.i.d (-10.39 bpm), and at 0.5 hours for pasireotide 1950 µg bid (-14.91 bpm). There were no subjects with QTcI or QTcF values that were increased more than 60 ms from baseline, or that exceeded 500 ms on Day 5, the last day of study treatment.

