14.11.2 Dose modifications for patients from protocol SOM230B2305

For patients who are unable to tolerate the protocol-specified dose level, dose adjustments are permitted in order to keep the patient on study drug. (Refer to [Table 14-13](#)). At any time during the study, patients with an early morning (between 8 and 10am) serum cortisol < 3 μ g/dl and a UFC measurement < LLN or symptoms suggestive of hypoadrenalinism (e.g. postural hypotension, nausea, and abdominal pain) and a UFC measurement <LLN should have their dose reduced.

During the roll-over, the investigator may reduce the dose in 300 μ g s.c. b.i.d. steps at any time if the patient does not tolerate the given pasireotide dose. The minimum dose to be administered will be 300 μ g s.c. b.i.d.. If the patient does not tolerate the 300 μ g s.c. b.i.d. dose, he/she will be withdrawn from the study.

These changes must be recorded on the Dosage Administration Record.

Table 14-13 Dose modification for AEs, excluding LFT increase, QT prolongation and hyperglycemia

Adverse event	Action
CTCAE grade \leq 2	No drug adjustments
CTCAE grade \geq 3 and assessed as study drug related	Reduce pasireotide to the next dose level. If the AE improves to grade \leq 2 before the next administration, increase dose back to the prior dose. If the dose is increased and the AE recurs at a grade \geq 3, the dose should be reduced again. The patient should stay on this lower dose and no further dose titrations are allowed. If the AE does not improve to grade \leq 2, the dose is to be reduced further. If the AE does not improve to grade \leq 2 on the minimum study dose, the treatment should be stopped. The patient should be discontinued and followed up for safety.

For the management of LFT increase, QT prolongation, and hyperglycemia refer to specific instructions provided in [Appendix 2](#), [Appendix 3](#) and [Appendix 4](#).

14.12 Appendix 12: Dose modification information for patients with Cushing's receiving pasireotide s.c in combination with cabergoline (SOM230B2411)

Table 14-14 Dose and treatment schedule

Study treatments	Pharmaceutical form and route of administration	Dose	Frequency and/or Regimen
Pasireotide	Subcutaneous	0.3mg, 0.6mg, and 0.9mg	Twice a day
Cabergoline	Oral	0.5mg or 1.0mg	Once a day

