- A single occurrence will be counted if there is ≤ 1 day gap between the end date of the preceding AE and the start date of the consecutive AE
- More than one occurrence will be counted if there is > 1 day gap between the end date of the preceding AE and the start date of the consecutive AE

For occurrence, the presence of at least one SAE / SAE suspected to be related to study treatment / non SAE has to be checked in a block e.g., among AE's in a \leq 1 day gap block, if at least one SAE is occurring, then one occurrence is calculated for that SAE.

The number of deaths resulting from SAEs suspected to be related to study treatment and SAEs irrespective of study treatment relationship will be provided by SOC and PT.

Adverse events of special interest / grouping of AEs

The specific categories of AEs of special interest list for SOM230 are listed in attachment 8.2.

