Study Procedures Criteria*	G08 Investigator failed to assess if the patient was continuing to receive clinical benefit at the visit.
Study Procedures Criteria	Investigator failed to document in eCRF if the patient was continuing to receive clinical benefit at the visit
Visit Schedule Criteria*	G10 Missed visit due to COVID-19
Visit Schedule Criteria*	G11 Visit done outside of study site due to COVID-19
Study Procedures Criteria*	G12 Assessment/ procedure changed due to COVID-19
Study Procedures Criteria*	G13 Drug supply method changed due to COVID-19
Investigation Product (IP) Compliance*	G14 Treatment not given due to COVID-19
Other Criteria*	G15 Discontinuation due to COVID-19
Study Procedures Criteria*	G16 Patient failed to adhere to protocol requirements or visit schedule
Study Procedures Criteria*	G17 Female patient of childbearing potential did not complete diary with dates and outcome of at-home urine pregnancy tests while on study treatment
Study Procedures Criteria	Site staff are allowed to work for limited hours due to Covid 19 restrictions

Category	Adverse Event Term
AESI Bradycardia related AEs	Atrial conduction time prolongation (PT)
	Atrioventricular block (PT)
	Atrioventricular block complete (PT)
	Atrioventricular block second degree (PT)
	Atrioventricular dissociation (PT)
	Bradycardia (PT)
	Central bradycardia (PT)
	Conduction disorder (PT)
	Defect conduction intraventricular (PT)
	Electrocardiogram PQ interval prolonged (PT)
	Electrocardiogram PR prolongation (PT)
	Electrocardiogram QRS complex prolonged (PT)
	Electrocardiogram QT prolonged (PT)
	Long QT syndrome (PT)
	Paroxysmal atrioventricular block (PT)
	Sinoatrial block (PT)
	Sinus bradycardia (PT)
AESI Coagulation related AEs	Blood fibrinogen decreased (PT)
	Blood thrombin decreased (PT)
	Blood thromboplastin abnormal (PT)
	Blood thromboplastin decreased (PT)
	Coagulation factor IX level decreased (PT)
	Coagulation factor V level decreased (PT)
	Coagulation factor VII level decreased (PT)
	Coagulation factor X level decreased (PT)
	Coagulation factor decreased (PT)
	Hypofibrinogenaemia (PT)
	International normalised ratio abnormal (PT)
	Prothrombin level decreased (PT)
	Prothrombin time prolonged (PT)
	Prothrombin time ratio decreased (PT)
	Thrombin time prolonged (PT)
AESI Gallbladder and biliary related AEs	Bile duct necrosis (PT)
	Bile duct obstruction (PT)
	Bile duct stenosis (PT)
	Bile duct stone (PT)

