8.2 LIST OF AES OF SPECIAL INTEREST

Category	Adverse Event Term
	Bile output abnormal (PT)
	Bile output decreased (PT)
	Bile output increased (PT)
	Biliary cirrhosis (PT)
	Biliary colic (PT)
	Biliary dilatation (PT)
	Biliary dyskinesia (PT)
	Biliary dyspepsia (PT)
	Biliary fibrosis (PT)
	Biliary fistula (PT)
	Biliary ischaemia (PT)
	Biliary tract disorder (PT)
	Bilirubin conjugated abnormal (PT)
	Bilirubin conjugated increased (PT)
	Bilirubin excretion disorder (PT)
	Bilirubin urine present (PT)
	Bilirubinuria (PT)
	Blood alkaline phosphatase abnormal (PT)
	Blood alkaline phosphatase increased (PT)
	Blood bilirubin abnormal (PT)
	Blood bilirubin increased (PT)
	Blood bilirubin unconjugated increased (PT)
	Cholangiogram abnormal (PT)
	Cholecystectomy (PT)
	Cholecystitis (PT)
	Cholecystitis acute (PT)
	Cholecystitis chronic (PT)
	Cholecystogram intravenous abnormal (PT)
	Cholecystogram oral abnormal (PT)
	Cholelithiasis (PT)
	Cholelithiasis migration (PT)
	Cholelithiasis obstructive (PT)
	Cholestasis (PT)
	Deficiency of bile secretion (PT)
	Endoscopy biliary tract abnormal (PT)
	Gallbladder disorder (PT)
	Gallbladder enlargement (PT)
	Gallbladder fibrosis (PT)
	Gallbladder fistula (PT)
	Gallbladder hypofunction (PT)

Category	Adverse Event Term
category	Gallbladder necrosis (PT)
	Gallbladder obstruction (PT)
	Gallbladder oedema (PT)
	Gallbladder operation (PT)
	Gallbladder operation (FT)
	Haemohilia (PT)
	Henatitis cholestatic (PT)
	Hepatobiliary disease (PT)
	Hyperbilirubinaemia (PT)
	laundice (PT)
	Jaundice cholestatic (PT)
	Jaundice extrahepatic obstructive (PT)
	Obstructive pancreatitis (PT)
	Perforation bile duct (PT)
	Pseudocholelithiasis (PT)
	Ultrasound biliary tract abnormal (PT)
	Urine bilirubin increased (PT)
	X-ray hepatobiliary abnormal (PT)
AESI Growth hormone deficiency related AEs	Blood growth hormone decreased (PT)
,	Insulin-like growth factor decreased (PT)
AESI Hyperglycemia-related AEs	Blood glucose increased (PT)
	Blood insulin decreased (PT)
	Diabetes mellitus (PT)
	Diabetes mellitus inadequate control (PT)
	Diabetes with hyperosmolarity (PT)
	Diabetic coma (PT)
	Diabetic hyperglycaemic coma (PT)
	Diabetic hyperosmolar coma (PT)
	Diabetic ketoacidosis (PT)
	Diabetic ketoacidotic hyperglycaemic coma (PT)
	Diabetic ketosis (PT)
	Fructosamine increased (PT)
	Glucose tolerance decreased (PT)
	Glucose tolerance impaired (PT)
	Glucose tolerance test abnormal (PT)
	Glucose urine (PT)
	Glycosuria (PT)
	Glycosylated haemoglobin increased (PT)

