	Hyperglycaemia (PT)
	Hyperglycaemic hyperosmolar nonketotic syndrome (PT)

Category	Adverse Event Term
	Impaired fasting glucose (PT)
	Impaired insulin secretion (PT)
	Increased insulin requirement (PT)
	Insulin-requiring type 2 diabetes mellitus (PT)
	Ketoacidosis (PT)
	Ketonuria (PT)
	Ketosis (PT)
	Ketosis-prone diabetes mellitus (PT)
	Monogenic diabetes (PT)
	Type 1 diabetes mellitus (PT)
	Type 2 diabetes mellitus (PT)
AESI Hypocortisolism related AEs	Adrenal insufficiency (PT)
	Adrenal suppression (PT)
	Adrenocortical insufficiency acute (PT)
	Cortisol decreased (PT)
	Cortisol deficiency (PT)
	Cortisol free urine decreased (PT)
	Glucocorticoid deficiency (PT)
	Glucocorticoids decreased (PT)
	Secondary adrenocortical insufficiency (PT)
	Steroid withdrawal syndrome (PT)
AESI Hypotension related AEs	Blood pressure ambulatory decreased (PT)
	Blood pressure decreased (PT)
	Blood pressure diastolic decreased (PT)
	Blood pressure immeasurable (PT)
	Blood pressure orthostatic abnormal (PT)
	Blood pressure orthostatic decreased (PT)
	Blood pressure systolic decreased (PT)
	Hypotension (PT)
	Mean arterial pressure decreased (PT)
AESI Hypothyroidism related AEs	Blood thyroid stimulating hormone decreased (PT)
	Hypothyroidism (PT)
	Myxoedema (PT)
	Myxoedema coma (PT)
	Secondary hypothyroidism (PT)
	Thyroid dermatopathy (PT)
	Thyroid stimulating hormone deficiency (PT)
	Thyroxine free decreased (PT)
	Tri-iodothyronine decreased (PT)
	Tri-iodothyronine free decreased (PT)

Category	Adverse Event Term
AESI Injection site reaction related AEs	Administration site abscess (PT)
	Immediate post-injection reaction (PT)
	Injection site atrophy (PT)
	Injection site bruising (PT)
	Injection site discolouration (PT)
	Injection site discomfort (PT)
	Injection site erosion (PT)
	Injection site erythema (PT)
	Injection site exfoliation (PT)
	Injection site granuloma (PT)
	Injection site haematoma (PT)
	Injection site haemorrhage (PT)
	Injection site hypersensitivity (PT)
	Injection site inflammation (PT)
	Injection site irritation (PT)
	Injection site necrosis (PT)
	Injection site nodule (PT)
	Injection site oedema (PT)
	Injection site pain (PT)
	Injection site pruritus (PT)
	Injection site rash (PT)
	Injection site reaction (PT)
	Injection site swelling (PT)
	Injection site urticaria (PT)
ESI Liver safety related AEs	Alanine aminotransferase abnormal (PT)
	Alanine aminotransferase increased (PT)
	Ammonia increased (PT)
	Aspartate aminotransferase abnormal (PT)

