	Aspartate aminotransferase increased (PT)
	Blood cholinesterase abnormal (PT)
	Blood cholinesterase decreased (PT)
	Computerised tomogram liver abnormal (PT)
	Gamma-glutamyltransferase abnormal (PT)
	Gamma-glutamyltransferase increased (PT)
	Guanase increased (PT)
	Hepatic enzyme abnormal (PT)
	Hepatic enzyme decreased (PT)
	Hepatic enzyme increased (PT)
	Hepatic function abnormal (PT)
	Hepatobiliary scan abnormal (PT)

Category	Adverse Event Term
	Hyperammonaemia (PT)
	Hypertransaminasaemia (PT)
	Liver function test increased (PT)
	Transaminases abnormal (PT)
	Transaminases increased (PT)
	Ultrasound liver abnormal (PT)
	Urine bilirubin increased (PT)
AESI Low blood cell related AEs	Anaemia (PT)
	Febrile neutropenia (PT)
	Haematocrit decreased (PT)
	Haemoglobin decreased (PT)
	Leukopenia (PT)
	Lymphocyte count decreased (PT)
	Lymphopenia (PT)
	Neutropenia (PT)
	Platelet count decreased (PT)
	Red blood cell count decreased (PT)
	Thrombocytopenia (PT)
AESI Pancreatitis related AEs	Abdominal compartment syndrome (PT)
	Blood trypsin increased (PT)
	Fat necrosis (PT)
	Hyperlipasaemia (PT)
	Lipase abnormal (PT)
	Lipase increased (PT)
	Pancreatic enzyme abnormality (PT)
	Pancreatic enzymes abnormal (PT)
	Pancreatic enzymes increased (PT)
	Pancreatitis (PT)
	Pancreatitis acute (PT)
	Pancreatitis haemorrhagic (PT)
	Pancreatitis necrotising (PT)
	Pancreatitis relapsing (PT)
	Peripancreatic fluid collection (PT)
AESI QT-prolongation-related AEs	Cardiac arrest (PT)
	Cardiac death (PT)
	Cardiac fibrillation (PT)
	Cardio-respiratory arrest (PT)
	Electrocardiogram QT interval abnormal (PT)
	Electrocardiogram QT prolonged (PT)
	Electrocardiogram repolarisation abnormality (PT)

Category	Adverse Event Term
	Long QT syndrome (PT)
	Loss of consciousness (PT)
	Sudden cardiac death (PT)
	Sudden death (PT)
	Syncope (PT)
	Torsade de pointes (PT)
	Ventricular arrhythmia (PT)
	Ventricular fibrillation (PT)
	Ventricular flutter (PT)
	Ventricular tachyarrhythmia (PT)
	Ventricular tachycardia (PT)

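### The growth hormone deficiency AESI group omits the diagnosis that names it, and four other AESI groups omit closely related terms, so some events can drop out of the AESI tables

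*SAP*

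**What the plan says.** SAP 7.4.1 states: "The specific categories of AEs of special interest list for SOM230 are listed in attachment 8.2". The same section requires AESI to be listed and summarised separately on the Safety Set, and codes events with the newest MedDRA version available at analysis. It gives no step for re-checking the fixed list against that version. SAP 7.1.1 and Protocol 10.5.3 name AESI, with AEs and SAEs, as the basis of the safety assessment. SAP 7.1.2 makes the analysis purely descriptive.

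Attachment 8.2 prints each group as a list of preferred terms. The group "AESI Growth hormone deficiency related AEs" has two: growth hormone decreased in blood, and insulin-like growth factor decreased. Entries in the other four groups include "Platelet count decreased (PT)" (low blood cell), "Blood pressure orthostatic decreased (PT)" (hypotension), "International normalised ratio abnormal (PT)" (coagulation) and "Atrioventricular block second degree (PT)" (bradycardia).

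Protocol 8.1.1 and 8.1.2.1 tell sites to prefer a diagnosis to its component signs, symptoms or laboratory findings, with anaemia rather than low haemoglobin as the example. Protocol 8.1.3 says AESI are defined through continuing review of the safety data.

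**The concern.** With a closed list, an event is counted under an AESI topic only if its preferred term is on the list. No hypothesis is tested, so these counts are themselves the result for each topic. If a topic's diagnosis is not listed, a site that follows the reporting instruction produces a record that the AESI table cannot pick up. A site that reports only the laboratory finding produces one that it can. The same clinical event is then counted or not according to how it was worded. A missing sibling term has the same effect on a smaller scale.

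**Working it through.** There is no plan figure to reproduce and no power or sample size involved. The check sets the printed groups in attachment 8.2 against each other and against the protocol.

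**Terms counted as printed:** growth hormone deficiency 2, low blood cell 11, hypotension 9, coagulation 15, bradycardia 17. All five groups run in unbroken alphabetical order.

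| Group | Main term listed? | Related term absent | Why its absence stands out |
|---|---|---|---|
| Growth hormone deficiency | No | Growth hormone deficiency | Hypocortisolism lists cortisol deficiency beside cortisol decreased; hypothyroidism lists hypothyroidism and TSH deficiency beside TSH decreased |
| Low blood cell | Yes: anaemia, leukopenia, lymphopenia, neutropenia, thrombocytopenia | Neutrophil count decreased; white blood cell count decreased | Count-decreased terms are given for lymphocytes, platelets and red cells |
| Coagulation | No single title term; prothrombin time prolonged and thrombin time prolonged are listed | INR increased | INR appears only as abnormal; this group gives thromboplastin as both abnormal and decreased, and other groups pair abnormal with increased for bilirubin, ALT, transaminases and lipase |
| Bradycardia | Yes: bradycardia, sinus bradycardia | AV block first degree; heart rate decreased | AV block is listed as unspecified, second degree, complete and paroxysmal; Protocol 1.2.1.2.2 reports "Both pasireotide doses decreased heart rate" |
| Hypotension | Yes: hypotension | Orthostatic hypotension | Two orthostatic blood pressure terms are listed; Protocol 14.11.2 refers to "symptoms suggestive of hypoadrenalinism (e.g. postural hypotension, nausea, and abdominal pain)" |

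**Growth hormone deficiency, followed through.** A site diagnoses the condition and, as Protocol 8.1.1 asks, reports the diagnosis rather than the low laboratory value. The event is coded to the diagnosis. Neither of the two listed terms matches, so it is not counted in the group.

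**Direction.** A missing term can only lower the count of its own group, never raise it.

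**Size.** Let *d* be the share of a topic's events coded to an unlisted term. At event level the AESI table then misses the share *d*. The documents do not give *d*, so it can lie anywhere from 0 to 1. At patient level the loss is no larger than the share of affected patients who have only unlisted terms, because a patient with any other listed term in the group is still counted.

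**Reach.** SAP 7.4.1 also tabulates all treatment-emergent AEs by system organ class and/or preferred term and lists them, whatever their AESI status. An event missed by an AESI group stays visible there.

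**The case against.** Five arguments on the other side deserve weight.

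- **Four groups do contain their main terms.** A reader might infer from the gaps that all five groups leave out their core terms. The documents do not support that: hypotension, bradycardia and the main cytopenia diagnoses are listed, and coagulation lists its principal prolonged-clotting terms. Only growth hormone deficiency lacks the term that names it.
- **The diagnosis rule covers part of the sibling gaps.** It steers a low neutrophil count to neutropenia, low white cells to leukopenia and a low heart rate to bradycardia, all listed. Postural hypotension is named in Protocol 14.11.2 only as a symptom of hypoadrenalism, and the hypocortisolism group lists adrenal insufficiency. Some first-degree AV block may be coded to the listed PR or PQ prolongation terms. The heart-rate text describes mean change in a QT study, not event coding. This makes the four sibling gaps minor. It does not remove them, since the rule applies only where a diagnosis is possible and the list itself carries count terms for three other cell lines. For growth hormone deficiency the same rule makes the gap worse.
- **MedDRA and the Investigator Brochure are not in the documents.** That each absent name is a separate preferred term is an assumption, and deliberate scoping cannot be excluded. This stands, and is why the remedy includes a dictionary check.
- **A row may have been lost from the printed table.** Nearby entries show character errors, and alphabetical order cannot reveal a dropped row. Nothing shows that one was dropped, and the sponsor can settle it from the source file.
- **Changing the list affects comparability with earlier interim AESI tables.** If those used the same list, a footnote deals with it.

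**Conclusion.** The point holds in full for growth hormone deficiency: as printed, diagnosed cases are left out of the AESI table that bears their name. It holds in a smaller form for the low blood cell, coagulation, bradycardia and hypotension groups, which omit closely related terms against the list's own pattern or against protocol text.

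Two stronger inferences should be resisted. The first is that the safety report as a whole under-counts these events. It does not, since the general AE tables and listings carry them. The second is that each group's total is too low on balance. That does not follow, because the bradycardia group, for example, also contains QT and QRS prolongation terms that add to its count.

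The conclusion assumes that the list is printed completely and that the absent names are valid preferred terms in the MedDRA version used. The size of the loss is unknown. This is worth correcting before lock, but it does not threaten the overall safety assessment.

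**What to change.** Before database lock:

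1. Add Growth hormone deficiency to its group in attachment 8.2.
2. Check every AESI group, including the sibling terms in the table above, against the MedDRA version in use and against all preferred terms observed in the database. Do this without looking at frequencies by indication or formulation, and add those that are valid preferred terms.
3. Record the MedDRA version of the final list.
4. Footnote any change from the list used at earlier interim analyses (SAP 2.3 schedules these from Q4 2017).

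This fits SAP section 2, which places analysis decisions before lock, and Protocol 8.1.3, which expects AESI definitions to evolve. The cost is an update to the attachment and the AESI lookup file, with no new data. Some AESI percentages may rise slightly, and comparison with earlier interim AESI tables will need the note. Made after lock, the same change could look data-driven.

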7.1.1 Primary endpoint

The assessment of safety will be based mainly on the frequency and severity of AEs, AESI and SAEs. See also Section 7.4.1.

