7.4.1 Adverse events (AEs)

Treatment emergent AEs are defined as those that started on or after the study medication, or those that started before study medication but worsened afterwards. AEs starting after 84 days following the last dose of pasireotide LAR treatment and after 30 days following the last dose of pasireotide s.c. treatment are not considered treatment emergent AEs. Summary tables for adverse events (AEs) have to include only AEs that started or worsened during the on-treatment period, the **treatment-emergent** AEs. However, all safety data

(including those from the post-treatment periods) will be listed and those collected during the post-treatment period are to be flagged.

The incidence of treatment-emergent adverse events (new or worsening from baseline) will be summarized by system organ class and/or preferred term, severity based on CTCAE grades (version 4.03), type of adverse event, relation to study treatment. The summary will include AEs regardless of study-drug relationship. The same analysis will be repeated for SAEs.

All treatment emergent AEs and SAEs will be listed. In this listing, the information on the relationship to study treatment will be included.

Adverse events will be coded using the Medical dictionary for regulatory activities (MedDRA) terminology using the latest available MedDRA version at the time of the analyses and the information of MedDRA version will be specified in the footnote of relevant outputs.

The following selection of AEs will be listed and summarized separately using Safety Set. AEs will be summarized for all grades and for grade 3 or 4 side-by-side.

- AEs
- SAEs
- AEs leading to study drug discontinuation
- AEs requiring dose adjustment or interruption
- AEs requiring additional therapy
- Adverse events of special interest (AESI)

For the legal requirements of ClinicalTrials.gov and EudraCT, two required tables on treatment- emergent adverse events which are not serious adverse events with an incidence greater than 5% and on treatment-emergent serious adverse events and SAE suspected to be related to study treatment will be provided by system organ class and preferred term on the safety set population.

If for a same patient, several consecutive AEs (irrespective of study treatment causality, seriousness and severity) occurred with the same SOC and PT:

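### The hypothyroidism AESI group in SAP 8.2 lists total and free T3 decreases but only the free T4 decrease, so an isolated event coded as a total T4 decrease would be left out of that summary

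*SAP*

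**What the plan says.** SAP 7.1.1 makes AESI part of the primary safety assessment: "The assessment of safety will be based mainly on the frequency and severity of AEs, AESI and SAEs". SAP 7.4.1 requires AESI to be listed and summarised separately and points to the attachment for their content: "The specific categories of AEs of special interest list for SOM230 are listed in attachment 8.2".

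Under "AESI Hypothyroidism related AEs" the attachment gives ten preferred terms. Three of them concern low circulating thyroid hormone: "Thyroxine free decreased (PT", "Tri-iodothyronine decreased (PT" and "Tri-iodothyronine free decreased (PT". No thyroxine term appears in any other AESI group.

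SAP 7.4.1 also says that events are coded "using the latest available MedDRA version at the time of the analyses". It does not say how the printed term list is to be checked against that version.

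**The concern.** The group treats the two hormones differently and gives no reason. A low T3 enters whether the coded term is unqualified or free. A low T4 enters only if the coded term is the free one. Because the AESI table is driven by a look-up of preferred terms, a term that is not on the list contributes nothing, however relevant the event is.

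What is at stake is the completeness of one AESI category in a descriptive long-term safety study. The general adverse event tables are not affected.

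**Working it through.** No sample size, power or error rate bears on this point. The check is a reading of the list, followed by the direction of the effect.

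**1. Contents of the group.** Six entries are conditions: hypothyroidism, secondary hypothyroidism, myxoedema, myxoedema coma, thyroid dermatopathy and TSH deficiency. Four are laboratory findings: blood TSH decreased, free T4 decreased, T3 decreased and free T3 decreased. 6 + 4 = 10 terms.

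**2. The four parallel low-hormone terms.** The unqualified T3 term is read here as total T3.

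| | Total | Free |
|---|---|---|
| T3 | listed | listed |
| T4 | not listed | listed |

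Three of the four are present.

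**3. Could another rule bring the missing term in?** SAP 7.4.1 has no standardised query, higher-level term or wildcard for AESI. SAP 6.1 allows further terms to be added to the deviation list from the collected data, but there is no such sentence for the AESI list. Protocol 8.1.3 says that AESI are defined by ongoing review of the safety data, yet the SAP states no step that updates attachment 8.2 before lock.

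**4. Does the list look as if it leaves out total-hormone terms on principle?** No. It keeps unqualified T3. The hypocortisolism group likewise lists both a general cortisol decrease and a decrease in urinary free cortisol.

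**5. Is a row simply missing from the copy?** In alphabetical order *Thyroxine decreased* would fall between "Thyroid stimulating hormone deficiency (PT" and "Thyroxine free decreased (PT", which are adjacent. The group shows no visible damage.

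**6. Direction and size.** Let *a* be the number of patients with at least one listed hypothyroidism term, *x* the number whose only such event is a total T4 decrease, and *N* the Safety Set.

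- Reported proportion: *a*/*N*
- With the term added: (*a* + *x*)/*N*
- Difference: *x*/*N*, which is never negative

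Neither *x* nor the final *N* is in the documents. As an illustration only, take *N* = 301, the number enrolled according to the Amendment 2 rationale in the protocol. Then *x* = 0, 1 or 3 shifts the overall proportion by 0, 1/301 = 0.33 or 3/301 = 1.00 percentage points. Within an indication and formulation cell the denominator is smaller, so one patient there shifts the proportion more.

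**The case against.** The best case against raising this has four parts.

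- **The dictionary premise.** *Thyroxine decreased* appears nowhere in the protocol or SAP, so its status as a preferred term cannot be confirmed from them. This stands, and the point is conditional on it.
- **Selective lists and lost text.** The SAP never promises to pair every total and free analyte. The low blood cell group, for instance, has lymphocyte and platelet count decreases but no neutrophil or white-cell count term. The Investigator Brochure, which protocol 8.1.3 cites for AESI, might explain the choice. Also, a sorted list stays sorted when a row is lost, and rows in the biliary group are garbled in the text of the public copy. So neither a deliberate omission nor a lost row can be wholly excluded. That is a reason to check the source first. It does not explain why unqualified T3 was kept.
- **Few events would escape.** Protocol 8.1.1 and 8.1.2.1 prefer a diagnosis to a laboratory term, and a result that belongs to an event already reported need not be recorded again. A clinically significant low T4 would often be recorded as hypothyroidism or secondary hypothyroidism, both of which are listed. This stands and limits the size.
- **Comparability.** SAP 2.3 plans interim analyses for the fourth quarters of 2017, 2019, 2021 and 2023. If earlier reports used the same list, adding a term at the end breaks the series slightly. This stands, and a footnote deals with it.

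A reader might infer two stronger claims. One is that most patients have pituitary disease, which would make the gap more important. The documents give no enrolment by indication, and the parent studies include dumping syndrome, melanoma, prostate cancer and neuroendocrine tumours. The other is that classification turns on which assay the local laboratory runs. Protocol 7.2.2 only permits local testing and says nothing about thyroid assays. Neither claim is supported.

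**Conclusion.** The asymmetry is on the face of SAP 8.2: three of four parallel low-hormone terms are listed, and no rule brings in the fourth. If *Thyroxine decreased* is a preferred term in the version used, and if the printed list is the one that will be programmed, an isolated event with that code is left out of the hypothyroidism AESI summary while its T3 counterpart is counted. The count can therefore only be understated.

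This is a minor point. The frequency is unknown and probably low, the event remains in the general treatment-emergent tables and listings, and SAP 7.1.2 tests no hypothesis. It would be wrong to conclude that safety events disappear from the report or that the primary adverse event summaries are biased.

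**What to change.** Before database lock:

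1. Check the hypothyroidism group against the source from which attachment 8.2 was taken, and have the coding team confirm *Thyroxine decreased* in the MedDRA version to be used.
2. Add the term to the group (10 to 11 terms). If the source shows a deliberate exclusion, state in the SAP why total T4 is left out while total T3 is kept.
3. If earlier interim reports used the ten-term list, add a footnote to the AESI table saying that the term was added.

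The cost is one row in the look-up table, a short coding check and possibly one footnote. No new data are needed. If the term proves not to be a current preferred term, the added row matches nothing and changes no result.
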